- Independence of residuals (Durbin-Watson test)

- Absence of multicollinearity (Variance Inflation Factor < 5)
- Normality of residuals (Shapiro-Wilk on residuals)

Reported: Adjusted MD (β coefficient) with 95% CI, R^2 , adjusted R^2 , F-statistic, overall model p-value

SAP-4.3 CSD Prevalence — Analysis

Unadjusted:

- Chi-square test or Fisher's exact test (if expected cell count < 5)
- Relative Risk (RR) with 95% CI
- Absolute Risk Reduction (ARR) and Number Needed to Treat/Harm (NNT/NNH)

Adjusted:

- **Binary logistic regression** at 6–8 weeks and at 6–7 months
- Covariates: same set as RMT regression model
- Variables with $p < 0.20$ in univariate analysis AND a priori confounders (age, parity, BMI, indication) included
- Model fit: **Hosmer-Lemeshow test**
- Multicollinearity: **Variance Inflation Factors (VIF)**
- Discrimination: **Area Under the ROC Curve (AUC)**
- Results expressed as adjusted **Odds Ratios (OR)** with 95% CI

SAP-5. SECONDARY OUTCOME ANALYSES

SAP-5.1 Continuous Secondary Outcomes

- Unadjusted: t-test or Mann-Whitney U as appropriate
- Adjusted: Multiple linear regression (same covariate set)
- Results: Mean difference or median difference with 95% CI

SAP-5.2 Binary Secondary Outcomes (Complications, Transfusion)

- Unadjusted: Chi-square or Fisher's exact test
- Results: RR, ARR, NNT/NNH with 95% CI

SAP-5.3 CSD Morphological Dimensions

Analyzed within the **CSD-positive subgroup only**:

- Depth, length, width: Mann-Whitney U test
- **CSD Volume** (ellipsoid formula): Mann-Whitney U test

SAP-5.4 Repeated Measures — RMT at 6 Weeks and 6 Months

Method: Linear Mixed-Effects Model (LME)

Model structure:

- Fixed effects: treatment group, time point (6 weeks vs. 6 months), treatment × time interaction
- Random effect: participant-level intercept (accounts for within-subject correlation)
- Covariance structure: Unstructured (preferred); compound symmetry if convergence issues

Interpretation:

- Significant interaction ($p < 0.05$): treatment effect differs across time points
- Non-significant interaction: main effects interpreted independently

SAP-5.5 Symptom Outcomes (Ordinal / Binary)

- Binary symptoms (spotting, dyspareunia): Chi-square or Fisher's exact test; RR with 95% CI
- **Paired temporal evolution** (6 weeks → 6 months within each group): **McNemar's test**
- Adjusted: Binary logistic regression

SAP-5.6 Hemoglobin Variation and Blood Loss

- ΔHb : t-test or Mann-Whitney U; mean difference with 95% CI

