Type of cesarean section	Scheduled vs. Intrapartum	Interaction term
Surgeon category	Senior vs. Resident Year 4–5	Interaction term

Test for interaction: Likelihood ratio test comparing models with and without the interaction term.

All subgroup analyses are exploratory and hypothesis-generating. No correction for multiple comparisons is applied to subgroup analyses; results will not drive primary conclusions.

Results will be presented in **forest plots**.

SAP-8. SENSITIVITY ANALYSES

Analysis	Method
SA-1: Per-Protocol population	Repeat primary analysis in PP population
SA-2: Intraoperative complication exclusion	Exclude participants with major intraoperative events (corporeal hysterotomy, hysterotomy extension > 2 cm)
SA-3: Multiple imputation for missing RMT	MICE — 5 scenarios: observed data, LOCF, best case, worst case, 6-week status carry-forward
SA-4: Inverse Probability Weighting (IPW)	Adjust for informative loss to follow-up
SA-5: Binary threshold analysis	Proportion with RMT < 2.5 mm and RMT < 3.0 mm; Chi-square test
SA-6: Complete case analysis	For comparison with imputed results

SAP-9. MULTIPLICITY AND TYPE I ERROR CONTROL

- **Primary outcomes:** $\alpha = 0.05$, two-sided, for each co-primary endpoint (RMT and CSD prevalence at 6 weeks and 6 months)
- **Secondary outcomes:** Exploratory; **Holm-Bonferroni correction** applied to control family-wise error rate
- **Unmeasured confounders:** **E-value** calculated to quantify the minimum strength of an unmeasured confounder needed to explain away observed associations

SAP-10. MISSING DATA STRATEGY

Data Type	Strategy
Primary outcome (RMT at 6 months)	Five imputation scenarios (MICE)
Secondary continuous outcomes	Complete case + sensitivity with imputation if > 10% missing
Binary outcomes	Complete case analysis

Symptom questionnaires	Linear mixed model (full information maximum likelihood)
------------------------	--

Missing data mechanism assessed by **Little's MCAR test**.

Participants lost to follow-up compared to completers on key baseline variables; reasons for dropout documented and reported.

SAP-11. PRESENTATION OF RESULTS

Results reported in accordance with **CONSORT 2010** guidelines:

- **Table 1:** Baseline characteristics (ITT population) — no p-values
- **Figure 1:** CONSORT flow diagram
- **Table 2:** Primary and secondary outcomes with between-group comparisons
- **Table 3:** Subgroup analysis (forest plots)
- **Table 4:** Multivariate analysis results

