3.2 Secondary Objectives

1. To compare **intraoperative parameters** between groups, including hysterorrhaphy duration, total operative time, visually estimated blood loss (PSTEV), calculated total blood loss (PSTC), number of additional hemostatic sutures, and intraoperative complications.
2. To assess **immediate postoperative outcomes**, including hemoglobin variation (ΔHb), transfusion requirement, early postoperative complications (endometritis, wound infection, parietal hematoma, thromboembolic events, surgical revision), and hospital length of stay.
3. To evaluate **medium-term gynecological symptoms** potentially attributable to CSD at 6 weeks and 6 months, including postmenstrual spotting, prolonged menstruation (> 7 days), dysmenorrhea, chronic pelvic pain, menometrorrhagia, and dyspareunia.
4. To compare **CSD morphological characteristics** between groups, including defect depth, length, width, and estimated volume using the ellipsoid formula.
5. To assess the **adjacent myometrial thickness (AMT)** and the **myometrial ratio ($\text{RM} = \text{RMT}/\text{AMT} \times 100$)** at both evaluation time points.
6. To identify **clinical and surgical predictors** of CSD formation and reduced RMT.
7. To evaluate the **mediating role** of CSD at 6 weeks on RMT at 6 months.

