9. OUTCOME MEASURES

9.1 Primary Outcomes

1. **Residual Myometrial Thickness (RMT)** at the uterine scar site, measured by **transvaginal ultrasonography (TVUS)** at **6–8 weeks** and **6–7 months** postoperatively (millimeters)
2. **Prevalence of Cesarean Scar Defect (CSD)** at **6–8 weeks** and **6–7 months** postoperatively, defined per **European Niche Task Force criteria (Jordan et al., 2019)** as a triangular anechoic indentation **≥ 2 mm** of the anterior uterine wall at the scar site

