10. DATA COLLECTION AND FOLLOW-UP SCHEDULE

Time Point	Assessment
Preoperative	Eligibility verification, informed consent, baseline NFS (CBC), demographics
Intraoperative	Randomization, surgical parameters, hysterorrhaphy duration, operative time, blood loss, complications
Postoperative Day 1	NFS (hemoglobin), vital signs, wound assessment
Discharge	Wound assessment, clinical evaluation, length of stay
6–8 Weeks postpartum	TVUS (RMT, CSD assessment), AMT, RM, clinical examination, standardized symptom questionnaire
6–7 Months postpartum	TVUS (RMT, CSD — PRIMARY ENDPOINT) , AMT, RM, CSD dimensions, volume, standardized symptom questionnaire

Ultrasonographic Examination Protocol

All TVUS examinations are performed:

- By a **dedicated, trained ultrasonographer per center, blinded to group allocation**
- Using **Samsung HS40 ultrasound system with EVN4-9 endovaginal probe (4–9 MHz)**
- With **standardized imaging parameters**

- With the **bladder empty**
- **Preferably in the follicular phase (Day 7–14 of the menstrual cycle)** to optimize defect visualization
- In the **mid-sagittal plane**: depth, length, and RMT measured; width measured in transverse plane
- **RMT measured perpendicular to the serosa at the thinnest point of the scar**

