7.5 CSD Volume

Formula: $V \text{ (mm}^3\text{)} = (\pi/6) \times \text{Length} \times \text{Width} \times \text{Depth}$

Analysis: Mann-Whitney U (in CSD-positive subgroup only)

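### Niche dimensions are tested between arms only in CSD-positive women, a group formed after randomization by a co-primary outcome, so the comparison should be descriptive

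*SAP*

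**What the plan says.** Secondary objective 4 in section 3.2 of the combined document is "To compare CSD morphological characteristics between groups". To serve it, SAP-5.3 restricts the analysis to the "CSD-positive subgroup only" and specifies "Depth, length, width: Mann-Whitney U test", with the same test for volume. In the combined document, section 7.5 covers volume only: "Analysis: Mann-Whitney U (in CSD-positive subgroup only". The restriction for depth, length and width therefore rests on SAP-5.3 alone.

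The subgroup is defined by an outcome. SAP-9 sets alpha "for each co-primary endpoint (RMT and CSD prevalence at 6 weeks and 6 months", and section 9.1 of the combined document defines a CSD as a "triangular anechoic indentation ≥ 2 mm of the anterior uterine wall at the scar site". Section 10 places the dimensions at the 6–7 month visit ("AMT, RM, CSD dimensions, volume, standardized symptom questionnaire").

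SAP-9 calls secondary outcomes exploratory and applies Holm-Bonferroni to them, and section 11 of the combined document also applies Holm-Bonferroni. Neither document labels the CSD-positive comparison as descriptive or non-randomized, says what effect it estimates, or adds a version in all scanned women.

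**The concern.** The trial exists because closure technique may change who develops a CSD. If it does, the CSD-positive women in the two arms are different selections from the randomized groups. A difference in their niche dimensions then mixes any effect on niche size with the effect on who is included. The selection is strong here because a woman enters the comparison through a threshold on niche size, and niche size is also what is tested.

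The clearest problem case is a technique that prevents shallow niches and leaves deep ones alone. Its remaining niches are deeper on average although no woman's niche became deeper. A p-value on that contrast could be read as evidence that the better technique produces worse niches. Under other mechanisms a real reduction in depth would be diluted.

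**Working it through.** **The plan's own figures.** For RMT (combined document, section 11): 2 × (1.96 + 0.842)² × 3.5² / 1.3² = 2 × 7.851 × 12.25 / 1.69 = 113.8, so 114 per group. With 30% loss, 114 / 0.70 = 162.9, so 163. Both match the stated values. No calculation is given for niche dimensions.

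**Inputs.** From section 11: 192 enrolled per group and 30% loss, so 192 × 0.70 = 134 scanned per arm. From section 9.1: CSD means at least 2 mm. Assumed, because the documents give neither a CSD rate nor a depth distribution: latent depth D is lognormal with median 1.7 mm and log-SD 0.6.

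**Shallow-niche mechanism: one technique prevents half of the 2–3 mm niches and deepens none.** With z(c) = ln(c/1.7)/0.6:
- P(D ≥ c) = 1 − Φ(z). For c = 2, z = 0.271 and P = 0.3932. For c = 3, z = 0.947 and P = 0.1719.
- E[D; D ≥ c] = 1.7 × exp(0.18) × Φ(0.6 − z) = 2.035 × Φ(0.6 − z). This is 1.2801 for c = 2 and 0.7417 for c = 3.
- Comparison arm: prevalence 39.3%; mean depth in positives 1.2801 / 0.3932 = 3.26 mm.
- Preventing arm: prevalence 0.3932 − ½(0.3932 − 0.1719) = 28.3%; mean depth in positives [1.2801 − ½(1.2801 − 0.7417)] / 0.2826 = 1.0109 / 0.2826 = 3.58 mm.
- Women in the test: 134 × 0.3932 ≈ 53 and 134 × 0.2826 ≈ 38.
- Mean over all scanned women, counting no niche as 0: 1.28 against 1.01 mm, which is the right direction.

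**How often the planned test is significant in the wrong direction** (simulated trials, Mann-Whitney in positives):

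| Two-sided level | Meaning | Rate |
|---|---|---|
| 0.05 | unadjusted | about 27% (repeat runs 27–29%) |
| 0.05/4 = 0.0125 | strictest Holm step, 4 tests | about 13% |
| 0.05/10 = 0.005 | strictest Holm step, 10 tests | about 7% |

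The documents do not state the size of the Holm family, so 4 and 10 are assumptions. Later Holm steps use looser levels, so for a given family size the strictest-step rate is a lower bound.

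**Other mechanisms, same lognormal.**
- Niches prevented at random: means in positives are equal (3.25 against 3.26 mm). Wrong-direction significance is about 2 to 3%, which is the nominal one-tail rate.
- Every depth reduced by 0.4 mm: means in positives are nearly equal (3.26 against 3.27 mm). The true reduction disappears, with no material reversal.
- Every depth reduced by 25%: the direction is right, but the test in positives is significant in only about 16% of trials.

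**A different distribution.** Take depth in positives as 2 + Gamma(2,1) mm, half of niches under 4 mm prevented, and comparison prevalence from 30% to 60%. Means in positives are 4.00 against 4.38 mm, and wrong-direction significance at unadjusted 0.05 is 21% to 39%. If only 30% of those niches are prevented (prevalence 40%), it is 11%. With a normal latent depth shifted uniformly by 0.5 or 1.0 mm, the direction holds but the contrast shrinks to about 30–37% of the shift.

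**The case against.** The strongest reply has four parts.

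- **Dimensions exist only where there is a niche.** A conditional summary is therefore the natural way to describe morphology, and objective 4 can be read that way. This stands, and it is a good reason to keep the table. It does not justify an unqualified between-arm test.
- **These outcomes are exploratory and Holm-corrected.** This also stands in part: the unadjusted 27% is not the rate that the plan would produce. Holm lowers how often the wrong result is called significant. It does not move the estimate, which still points the wrong way in that scenario.
- **Reversal needs a particular mechanism.** Correct. A reader might infer that the planned test will reverse the effect. The documents do not support that, because they contain no depth data, and random prevention or a uniform shift gives no reversal.
- **The primary prevalence test already captures the benefit.** A reader might compare 16% power in positives with 87–88% for an all-women rank test under a 25% reduction, and conclude that the plan would miss the benefit. It would not. The planned co-primary prevalence test alone has about 85–86% power there and reaches the same verdict as the all-women test in 95% of trials. In the shallow-niche scenario it has more power than the all-women test (49% against 35%). The all-women test is mostly a second look at prevalence.

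**Conclusion.** The concern holds as a limit on interpretation. As written, SAP-5.3 (four dimensions) and section 7.5 (volume) attach a between-arm test to groups that randomization does not make comparable if technique affects CSD. The result can be right in direction, attenuated or reversed, and the trial's p-value will not show which. In the adverse illustration the apparent disadvantage is about 0.32 mm (3.58 − 3.26). It is significant in about 7% to 27% of trials across the three levels shown. All of this rests on the assumed depth distribution and mechanism. If technique does not change who has a CSD, this bias does not arise.

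A reader might go further and infer that the trial's main conclusions are at risk. They are not. CSD prevalence is not analysed conditionally on CSD, and RMT is defined at the scar line when there is no niche (combined document, section 2), so neither co-primary endpoint depends on this subgroup. Severity is minor to moderate, because these are exploratory secondary outcomes.

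**What to change.** In SAP-5.3 and in section 7.5 of the combined document, report depth, length, width and volume in CSD-positive women as descriptive, non-randomized summaries by arm. Omit between-arm p-values and show CSD prevalence directly beside them.

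If a between-arm test is kept for depth and volume, and for length and width in the same way, run the Mann-Whitney test on all scanned women with no niche ranked lowest. A rank test needs only that ordering and no numerical value for an absent niche. State that the test measures presence and size together and largely overlaps the co-primary prevalence test.

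The cost is SAP wording, plus one recoded variable per dimension if tests are kept. No new data are needed. The SAP describes itself as finalized before database lock and unblinding, so the change should be documented and justified as SAP-1 requires. The downside is that the all-women result does not isolate size among women with a niche, which is why the descriptive table stays.

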11. SAMPLE SIZE CALCULATION

The sample size was determined based on the primary outcome — **RMT at 6 months** — using the standard formula for comparison of two independent means:

$$n = \frac{2 \times (Z_{\alpha/2} + Z_{\beta})^2 \times \sigma^2}{\Delta^2}$$

Parameters:

- Two-sided significance level: $\alpha = 0.05$ ($Z_{\alpha/2} = 1.96$)
- Statistical power: 80% ($Z_{\beta} = 0.842$)
- Conservative standard deviation: **$\sigma = 3.5$ mm**
- Minimum clinically meaningful difference: **$\Delta = 1.3$ mm**

Base sample size: 114 participants per group

Adjustment for loss to follow-up:

Based on local postpartum follow-up data and published literature, a **30% loss to follow-up rate** was anticipated:

$$n_{adjusted} = \frac{114}{1 - 0.30} \approx 163 \text{ per group}$$

Total enrolled: 384 participants (192 per group)

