7. SECONDARY OUTCOME ANALYSES

7.1 Repeated Measures — Linear Mixed-Effects Model (LME)

Fixed effects: Treatment, time (6w vs. 6m), treatment × time interaction

Random effect: Participant intercept

Covariance: Unstructured (preferred); compound symmetry if needed

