13. SOFTWARE

Software	Use
SPSS v26.0 (IBM)	Primary analyses
R v4.3 (R Foundation)	LME, mediation, bootstrap, reproducibility, imputation
R packages	lme4, mice, mediation, ggplot2, tableone, pROC, irr, MKmisc

Reproducibility: All R scripts version-controlled and archived. Random seed: `set.seed(2025)`.

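### The two-visit RMT mixed model pairs a random intercept with an unstructured covariance, which is one parameter too many, and its fallback assumes equal variances that the documents do not support (minor; secondary analysis)

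*SAP*

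**What the plan says.** SAP-5.4 plans a linear mixed model for RMT. The fixed part consists of the allocated group, the visit (two levels) and their product. To this the plan adds "Random effect: participant-level intercept (accounts for within-subject correlation". Then, as a further item with no link to the intercept, it states "Covariance structure: Unstructured (preferred); compound symmetry if convergence issues".

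The rule for reading the results covers the interaction test and, when that is not significant, the main effects. It does not list a separate treatment effect at each visit.

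Section 7.1 of the SAP in the combined document has the same combination. It lists "Random effect: Participant intercept" and, for the second component, gives "Covariance: Unstructured (preferred); compound symmetry if needed", so the trigger for the fallback is looser there.

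Neither text says whether the covariance structure belongs to the residuals or to the random effects, whether the intercept is removed under the unstructured option, or whether the fallback allows a different variance at each visit. For RMT variability the documents offer only "Conservative standard deviation: $\sigma = 3.5$ mm", used to size the 6-month comparison. They give no 6-week SD and no correlation between visits.

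**The concern.** A random intercept and an unstructured residual covariance both describe the correlation between a woman's two measurements. With only two visits they compete for the same information, so software may report non-convergence or a singular fit because of how the model is written rather than because of the data. That report is the SAP-5.4 condition for switching to compound symmetry, which forces RMT to vary equally at 6 weeks and 6 months. Scar healing between those visits could change the spread in either direction. If it does, standard errors from the fallback are wrong.

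The primary objective includes whether the effect is stable over time, and this model is the plan's only between-group test of that for RMT. As the text stands, the analyst would have to settle the structure after seeing the data, which SAP-1 sets out to avoid.

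**Working it through.** **Inputs.** Two visits, a random intercept, and unstructured or compound-symmetry covariance (SAP-5.4; combined document, SAP section 7.1). SD 3.5 mm, difference 1.3 mm, two-sided 0.05, 80% power, 30% loss, 384 enrolled (combined document, protocol section 11). Assumed because the documents give neither: a separate SD at each visit, and a between-visit correlation of 0.4 to 0.7.

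**The plan's own figure.** The documents give no number for the mixed model. The sample size that shares its inputs reproduces: 2 × (1.96 + 0.842)² × 3.5² / 1.3² = 113.8, so 114 per group; 114 / 0.70 = 162.9, so 163.

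**Parameter count.** With intercept variance τ² and residual covariance R, the estimable quantities are

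- variance at 6 weeks = τ² + R11
- covariance = τ² + R12
- variance at 6 months = τ² + R22

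That is four parameters for three quantities (rank 3). Adding c to τ² and subtracting c from every element of R changes nothing. In one simulated data set (192 per group, SDs 5.0 and 3.5 mm, correlation 0.6, 30% missing at 6 months), τ² = 0, 2, 4, 6 and 8 all gave REML log-likelihood −1225.433912. For example, τ² = 0 with R = (26.396, 10.632, 12.303) is the same model as τ² = 8 with R = (18.396, 2.632, 4.303).

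| Specification | Parameters | Rank |
|---|---|---|
| Intercept + unstructured | 4 | 3 |
| Intercept + compound symmetry | 3 | 2 |
| Unstructured alone | 3 | 3 |
| Compound symmetry alone | 2 | 2 |

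So the fallback is redundant too if the intercept stays. If the covariance line refers instead to the random effects, a single intercept has a 1×1 covariance. Unstructured and compound symmetry then coincide, the line has no content, and a model with the usual independent, equal-variance residuals already assumes equal variances.

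**Cost of equal variances, complete data.** Compound symmetry estimates one variance, (s1² + s2²)/2, and the covariance k.

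- Interaction: per-woman variance of the change is 2 × (s1² + s2²)/2 − 2k = s1² + s2² − 2k, the true value. Ratio of model to true SE 1.000, type I error 5.0%.
- Average over visits: [2 × (s1² + s2²)/2 + 2k]/4 = (s1² + s2² + 2k)/4, again the true value. Type I error 5.0%.
- 6-month contrast: ratio r = √[(s1² + s2²)/2] / s2, and type I error = 2[1 − Φ(1.96 r)]. For 3.0/4.0 mm, r = √12.5 / 4.0 = 0.884, giving 8.3%.

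**With 30% missing at 6 months, completely at random.** S is the true covariance. V is the compound-symmetry matrix minimising 0.7[log|V| + tr(V⁻¹S)] + 0.3[log V11 + S11/V11]. E has 1/V11 in its first cell and zeros elsewhere. A = 0.7V⁻¹ + 0.3E and B = 0.7V⁻¹SV⁻¹ + 0.3ESE. For a contrast c, r = √[c′A⁻¹c / c′A⁻¹BA⁻¹c], and type I error follows as above.

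| SD 6 wk / 6 mo (mm, assumed) | 6-mo contrast, complete data | Interaction or average, 30% loss | 6-mo contrast, 30% loss |
|---|---|---|---|
| 3.2 / 3.8 | 7.0% | 5.7% | 7.5% |
| 3.0 / 4.0 | 8.3% | 6.2% | 9.2% |
| 2.5 / 4.5 | 11.3% | 7.4% | 13% |
| 4.0 / 3.0 | 2.1% | 4.0% | 1.8% |

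Varying the correlation from 0.4 to 0.7 moves these by less than 0.3 percentage points. With the 6-month SD held at 3.5 mm and complete data, 6-week SDs of 3.0, 3.5 and 4.0 mm give 6.8%, 5.0% and 3.5% for the 6-month contrast.

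**The case against.** The strongest reply has four parts.

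1. *Only the split between intercept variance and residual covariance is unidentified.* This stands. A reader might infer that the model cannot be fitted or that its treatment estimates are invalid. Neither follows: the total covariance, the fixed effects and their standard errors are unique.
2. *The larger error rates belong to a contrast that SAP-5.4 does not list.* This also stands. With complete data the interaction and the averaged effect are exact under compound symmetry, so 7.0% to 11.3% must not be attached to the treatment × time test. One gap remains. If the main effect were read as the treatment coefficient at a reference visit, it would be visit-specific and exposed; the SAP does not state the coding.
3. *RMT at each visit is tested elsewhere.* SAP-4.1 compares the groups with two-sample tests, and the adjusted regression in SAP-4.2 uses 6–7-month RMT only. Neither pools variance across visits, so no primary result depends on this model.
4. *Nothing shows that variances differ or that the fallback will be used.* Correct. Section 13 of the combined document lists "lme4, mice, mediation, ggplot2, tableone, pROC, irr, MKmisc", and a reader might infer from lme4 that compound symmetry will be used by default. The list does not tie a package to this model, the April 2026 SAP names no package, and the switch is conditional in both texts.

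What the reply does not remove is that both written options are over-parameterised, and that the defect can trigger its own fallback.

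**Conclusion.** The specification is wrong as written, in both documents, and the consequence is small. If the fallback is used and the variances differ, the tests that SAP-5.4 does list stay at 5.0% with complete data and move to roughly 4.0% to 7.4% with 30% loss over the assumed SD pairs. Only a 6-month contrast drawn from the model would be seriously off, at about 1.8% to 13%. The direction is unknown, and equal SDs would mean no error at all.

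These sizes rest on assumed SDs, loss completely at random and large-sample theory. The 2.5/4.5 mm case is extreme: its variance ratio is 20.25/6.25 = 3.2. The parameter count rests on no assumption beyond reading the covariance line as residual covariance, and the alternative reading leaves that line empty.

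Severity is minor: a correction worth making because it is free, in a secondary analysis that leaves the primary 6–7-month regression unaffected.

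**What to change.** In SAP-5.4 and in section 7.1 of the combined document, state one model: RMT on treatment, visit and treatment × visit, with an unstructured 2×2 within-woman covariance, fitted by REML, and no random intercept. SPSS MIXED with a REPEATED statement, or nlme::gls in R, fits it; name whichever will be used.

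Delete the compound-symmetry fallback, which also removes the mismatch between the two trigger wordings. Heterogeneous compound symmetry is no substitute: with two visits it has the same three parameters and is the same model. Three covariance parameters from 384 women, about 384 × 0.70 = 269 of them with a 6-month scan on the planned loss, should not need a fallback.

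The cost is a few lines of SAP text and possibly a different R function. No data, sample size or primary analysis changes.

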3. OBJECTIVES

3.1 Primary Objective

To compare the **residual myometrial thickness (RMT)** at the uterine scar site between single-layer and double-layer hysterorrhaphy techniques, and to compare the **prevalence of cesarean scar defect (CSD)**, at **6 weeks and 6 months** following primary cesarean section, as measured by transvaginal ultrasonography, in order to assess both early scar formation and the stability of the effect over time.

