6.2 CSD Prevalence Analysis

Unadjusted: Chi-square or Fisher's exact test → RR, ARR, NNT/NNH with 95% CI

Adjusted: Binary logistic regression at 6–8 weeks and 6–7 months

- Variables: $p < 0.20$ in univariate + a priori confounders
- Fit: Hosmer-Lemeshow test
- Multicollinearity: VIF
- Discrimination: AUC (ROC curve)
- Results: Adjusted OR with 95% CI

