12. MISSING DATA

Little's MCAR test to assess missing data mechanism.

Outcome	Strategy
RMT at 6 months	Five-scenario MICE (SA-3)
Secondary continuous	Complete case + MICE if > 10% missing
Binary outcomes	Complete case
Symptom questionnaires	Full information maximum likelihood (FIML) via mixed models

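### Stability of the effect over time is part of the primary objective, but the plan has no estimate or criterion for it for RMT and no between-visit comparison for CSD

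*SAP*

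**What the plan says.** Protocol section 3.1 sets RMT and CSD prevalence at both visits as the primary objective, "in order to assess both early scar formation and the stability of the effect over time". Protocol section 9.1 and SAP-4 list both endpoints at both visits.

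**RMT.** SAP-5.4 fits a linear mixed model with treatment, time and their interaction. An interaction p-value below 0.05 is read as an effect that differs between visits. Otherwise the instruction is "Non-significant interaction: main effects interpreted independently". Section 7.1 of the SAP in the combined document has the same model without any reading rule. Neither place asks for a confidence interval for the change in effect, sets a margin, or gives power for the interaction. SAP-4.1 reports mean differences with intervals, and the adjusted model in SAP-4.2 is specified for 6–7 months only. Lin's coefficient and Bland-Altman analysis (SAP-6.4) describe agreement of RMT between visits, not change in the treatment effect.

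**CSD.** SAP-4.3 and section 6.2 plan chi-square or Fisher tests and "Binary logistic regression at 6–8 weeks and 6–7 months", with no group-by-visit term. McNemar's test (SAP-5.5) is reserved for symptoms. The missing-data strategy for binary outcomes is "Complete case" (SAP-10; section 12), against an anticipated 30% loss (protocol section 11).

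**The concern.** Asking whether an effect is stable means asking how much it changes between visits. A p-value split does not answer that. A non-significant interaction fits both no change and a sizeable change measured imprecisely, and the trial was sized for one between-arm difference at 6 months, not for a change in that difference. A report that follows SAP-5.4 would have no planned statement of how much fading the data rule out.

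For CSD, the reader would set two separately estimated effects side by side. They may come from partly different women, and nothing planned gives the uncertainty of their difference. An apparent fading or persistence could partly reflect who returned. That part of the primary objective would be left to visual comparison.

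**Working it through.** **Inputs** (protocol section 11): two-sided α 0.05, power 80%, SD 3.5 mm, meaningful difference 1.3 mm, 30% loss, 192 enrolled per group.

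**The plan's own figure.** n = 2 × (1.96 + 0.842)² × 3.5² / 1.3² = 113.8, so 114 per group. 114 / 0.70 gives 163. Both are reproduced. The documents do not explain the step from 163 to 192, but it does not affect this point. The expected evaluable number is 192 × 0.70 = 134.4, taken as 134 per arm.

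**Precision of the interaction.** With equal SDs at both visits, the treatment-by-time term is a two-arm comparison of change scores:
- SD of change = 3.5 × √(2(1 − ρ))
- SE = SD of change × √(2/134)
- 95% half-width = 1.96 × SE
- power for a change of 0.65 mm (half of 1.3) ≈ Φ(0.65/SE − 1.96)

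The between-visit correlation ρ is not in the documents, so a range is assumed. Example at ρ = 0.5: SD of change 3.50, SE 0.428, 0.65/0.428 − 1.96 = −0.44, power 0.33.

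| ρ (assumed) | SD of change, mm | SE, mm | 95% half-width, mm | Power for 0.65 mm | Missed |
|---|---|---|---|---|---|
| 0.3 | 4.14 | 0.506 | 0.99 | 0.250 | 75% |
| 0.5 | 3.50 | 0.428 | 0.84 | 0.330 | 67% |
| 0.7 | 2.71 | 0.331 | 0.65 | 0.501 | 50% |
| 0.8 | 2.21 | 0.270 | 0.53 | 0.671 | 33% |
| 0.9 | 1.57 | 0.191 | 0.37 | 0.925 | 7.5% |

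Power passes 50% at ρ of about 0.70 and reaches 80% at about 0.85. For ρ up to about 0.7, an interval centred on no change still reaches a loss of 0.65 mm.

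**Sensitivity.**
- The mixed model also uses women seen only at the first visit. With 192 per arm at 6 weeks and 134 at 6 months, the variance is 2 × 3.5² × [(1 − ρ²)/134 + (1 − ρ)²/192], and power over the same ρ values is 0.274, 0.353, 0.519, 0.685 and 0.929. Little changes.
- At ρ = 0.5 and 134 per arm, power is 0.43, 0.57 and 0.76 if the true SD is 3.0, 2.5 or 2.0 mm.
- Complete loss of the 1.3 mm effect is detected with power 0.73 at ρ = 0.3, 0.86 at 0.5 and 0.975 at 0.7.

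**CSD.** No planning rates are stated, so no corresponding figure follows from the documents. The gap is structural: no planned analysis compares the CSD effect at the two visits.

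**The case against.** The strongest reply is that the plan already reports the ingredients. Effects are estimated at each visit with intervals, and section 14 adds individual RMT trajectories, so a fall from 1.3 to 0.65 mm would be visible in the estimates. This stands in part: what can be missed is statistical recognition of the change, not the two estimates. But two separate intervals do not give the interval for their difference, since the visits share women and are correlated.

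A second reply is that differing samples are partly handled. SA-1 repeats the primary analysis in women with a valid 6-month scan, and SA-4 weights for informative loss and is not confined to RMT. That also stands, but neither compares the visits.

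A third is that the follow-up schedule (protocol section 10) marks the 6–7 month scan as the primary endpoint and that the mixed model sits among secondary analyses. Yet section 3.1 gives stability as a purpose of measuring at both visits.

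A reader might infer more than the documents support:
- *That the SAP equates non-significance with stability.* It does not say so. It prescribes how main effects are read and gives no other criterion.
- *That loss of half the RMT effect would usually be missed.* At the planning SD and 134 per arm this holds only for correlations below about 0.70. It also fails at ρ = 0.5 if the SD is 2.5 mm or less, and the protocol calls 3.5 mm conservative.
- *That the miss rates apply to CSD.* They are for RMT only.
- *That a 20% chance of missing complete loss is a special weakness.* With 114 per arm and ρ = 0.5, the change-score SD is 3.5 mm, so this is simply the 80% design power. With 134 per arm the miss rate is 14%.

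**Conclusion.** The concern holds in this form: stability is in the primary objective for both endpoints, RMT has only a p-value split with no interval for the change and no criterion, and CSD has no between-visit comparison of the treatment effect. For RMT, the chance of missing a halving of the effect runs from about 75% at a correlation of 0.3 to 7.5% at 0.9. This rests on an SD of 3.5 mm at both visits, 134 evaluable women per arm and an assumed correlation. The size of the risk depends on that correlation, but the gap does not: even where power is good, a p-value does not say how much change the data exclude. For CSD the conclusion is structural and carries no number.

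**What to change.** 1. In SAP-5.4, replace the significant/non-significant reading rule. Report the treatment effect at each visit and their difference (6–7 months minus 6–8 weeks) with 95% CI, whatever the p-value. State the same in section 7.1, which now has no reading rule. The difference and its interval are the main addition, since per-visit effects are largely planned already.
2. Describe the RMT effect as stable only if that interval excludes a loss of a pre-stated amount smaller than 1.3 mm, for example 0.65 mm. Otherwise report that change over time is not determined. A margin of 1.3 mm itself would allow the word when nearly all of the planned effect could have gone.
3. In SAP-4.3 and section 6.2, add one repeated-measures binary model for CSD (GEE or mixed logistic; group, visit, group × visit) using all women with at least one scan. Report the ratio of the two visit-specific effects with 95% CI. Keep the per-visit models.

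Make the change before database lock, or record it as a justified deviation as SAP-1 provides. The cost is some wording and one extra model on data already scheduled. The real downside is that the report may have to say stability was not shown. With a 0.65 mm margin and 134 per arm, an observed change of zero would not be clearly enough at correlations up to about 0.7. At 0.8 the observed loss would have to be below about 0.65 − 0.53 = 0.12 mm.
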